MRI and MR spectroscopy will be performed twice during this prospective study (baseline and final 6-month visit) using FDA-approved devices and pulse sequences. A standard MRI questionnaire will be administered to all potential study subjects, and no study subject with a contraindication to MR testing will be admitted to the study. There are no known foreseeable risks associated with exposure to MRI, provided patients are appropriately screened and there are no metallic implants (i.e. vascular clamps or pacemakers). All potential subjects will be carefully screened for the presence of such implants or any other contraindication to MRI, prior to each exam. No study subject with a contraindication to MR testing will be admitted to the study. Some subjects report some claustrophobia during MRI scans. If a patient expresses any discomfort whatsoever during the scan, the procedure will be aborted and not repeated without his/her full consent.

Risks of Stool Collection:

Stool will be collected using a stool collection kit that contains some special preservatives to make sure they are stable over time. If skin comes into contact with these preservatives, they could irritate the skin. The preservative can simply be washed off with soap and water.

Risks of Genetic Testing

Genetic information that results from this study does not have medical or treatment importance at this time. However, there is a risk that information about taking part in a genetic study may influence insurance companies and/or employers regarding a subject's health. To safeguard the privacy of our subjects, genetic information obtained in this study will not be shared or made available to be placed in the medical record. Taking part in a genetic study may also have a negative impact on family or other personal relationships.

We will in no way discourage use of any medications that are clinically indicated for the subject. Subjects will be discontinued from the study if they start a medication that is known to affect liver fat, including methotrexate, amiodarone, oral steroids or SERMs (such as tamoxifen). The subject will be able to continue in the study if they initiate other medications that are not known to affect liver fat content.

B. Protection Against Risk

In addition to the formal safety monitoring plan described below, the procedures to protect against or minimize potential risks include the following: (1) the assignment of unique study subject numbers to patients, (2) the use of these primary identifiers throughout the study, (3) storage of information in locked file cabinets, and (4) access limited to study personnel for these file cabinets and data. The blood draws will be performed by trained staff who are certified to draw blood. We are performing a physical examination and routine laboratory tests prior to allowing anyone to enter the protocol to ensure that subjects are medically stable. Close monitoring of patients throughout the study will ensure that adverse effects from our interventions. All study subjects will be instructed on how to contact study clinicians in the case of an emergency. The PI ([name]) will be available by pager at all times during the study to answer any questions or address any concerns that a subject may have.

Participants will also be required to sign a consent form prior to entering into the study. All recruitment materials will be approved by the MGH Institutional Review Board prior to initiating the study.

C. Anticipated Benefits to Subjects

There is no expected benefit to participation in this study. If one is assigned to receive aspirin therapy, it is possible that their amount of liver fat may decrease and their cardiovascular risk and/or waist fat may decrease during the study. However, those effects are not promised or guaranteed. If benefits occur, there is no way to know how long they will last.

Participants will have thorough physical exams while in this study. If a medical condition is discovered, one will be referred to your physician. It is possible that information learned from this study may help improve therapy for people who are obese. Further, all participants will receive information about their metabolic and nutritional health at the screening visit, consistent with current recommendations for clinical trials in patients with NAFLD/NASH⁸. The risk involved in study participation is thus thought to be balanced by the possible benefits to participants.

IX. INDEPENDENT MONITORING OF SOURCE DATA:

Monitoring of Source Data:

The principal investigator will be reviewing each subject's data periodically throughout the duration of the study for quality, validity and integrity assurance and for adherence to the IRB approved protocol. In addition, the study coordinators will monitor subject documents on an ongoing basis. All source data will be organized and filed into subject binders. Any pertinent notes to file regarding the subject will be documented by the study coordinator and kept in the applicable subject binder. All subjects will be assigned a study identification number.

Data Quality Control Monitoring:

Data will be recorded on specified Case Report Forms retained at Massachusetts General Hospital through REDCap. REDCap is a secure, web-based application designed to support data capture for research studies. The system was developed by a multi-institutional consortium initiated at Vanderbilt University and designed to comply with HIPAA regulations. Data forms from REDCap can be automatically exported into a spreadsheet to which additional data

(laboratory studies, etc) can be added. Forms that have missing or inconsistent data will also be entered into the database, except that a missing value indicator will take the place of the missing or inconsistent information. A missing information form will be filled out to indicate the items that are missing. Any paper data forms will be filed in a dedicated locked filing cabinet organized by subject code number. To ensure data entry accuracy, peer review of source documentation and case report forms in REDCap will be completed following MGB Study Data Management and Quality Assurance Plan Guidelines. The data will reside on the secure Massachusetts General Hospital secure file server which is within the secure Partners firewall, and which is backed up every day, with periodic secure back-ups off-site.

A physician will be available at all times during the study by pager to answer any questions a patient might have. The physician will arrange to immediately see every patient with a concern. All efforts will be made to protect the confidentiality rights of the study subjects who will be referred to by code numbers only. Confidentiality of the patients will always be of paramount importance to study investigators. No data on patients will be shared with persons other than those directly involved in the study, except at the documented request of the patient. Samples that are sent to laboratories outside of MGH will be labeled with a non-identifying numeric code.

Safety Monitoring:

A Data Safety Monitoring Board (DSMB) will be established at Massachusetts General Hospital consisting of independent members, who will review all study procedures, adverse events, protocol violations, protocol exceptions and deviations as well as study inclusion and exclusion criteria. The DSMB will also review safety monitoring blood tests and study data as available. The DSMB members will consist of independent experts in the field with experience in the conduct of clinical trials, statistical knowledge and independence from the direct management of the clinical trial. These members include Drs. [name] MD (Professor of Medicine, Massachusetts General Hospital), [name] MD (Professor of Medicine, Massachusetts General Hospital), and [name], PhD (Professor of Anesthesiology, Brigham and Women's Hospital). In addition, the PI ([name]) and the co-investigator team (Drs. [name], [name] and [name]) will participate in a portion of the meeting as non-voting members. The DSMB and the study investigators will meet together at least once every 6-9 months, or more often as needed, and the chair ([name]) will be the contact person for the DSMB and will be responsible for overseeing the meetings, developing the agenda and summarizing the findings of the meeting.

All treatment-related serious adverse events will be reported to the DSMB within 24h of occurrence. In addition, the chair may call ad hoc meetings. The Board will be provided with reports of serious adverse events as they occur and the chair of the committee has the responsibility of calling an ad hoc meeting if the type or frequency of the serious adverse events is of concern. In addition, an ad-hoc meeting may be called to evaluate whether a subject should be unblinded due to safety concerns or a serious adverse event (SAE). If a study subject is unblinded, the PI will not be made aware of the treatment assignment.

The Board may request additional information from the Investigator in the course of its review. The Investigator shall not be present for part of the Board's meeting.

Safety assessments:

3. CBC: at screening, baseline, and 6 months (and hematocrit at 3 months)
4. Pregnancy testing at all visits

The physician investigator will review all laboratory results in a timely manner.

Subjects will be discontinued if they develop:

1. Bleeding event resulting in hospitalization or decrease in hematocrit by >20% from baseline
2. Decrease in hematocrit by >20% from baseline
3. Positive pregnancy test
4. Severe / intolerable side effects of aspirin
5. Development of malignancy
6. Initiation of the following medications: methotrexate, amiodarone, systemic steroids or tamoxifen

Safety Monitoring:

1. Review of all adverse events (expected, unexpected and serious)
Severity, frequency and reporting protocol adherence
2. Review safety assessments described above
3. Review CBC (or hematocrit) results with unblinded monitor
4. Recruitment, enrollment (adherence to eligibility criteria)
5. Dropout rates
6. Protocol changes

Discontinuation Guidelines:

1. Individual:
 - a. Positive pregnancy test
 - b. Severe / intolerable side effects of aspirin
 - c. Bleeding in the gastrointestinal tract
 - d. Decrease in hematocrit by >20% from baseline
 - e. Development of malignancy
 - f. Initiation of the following medications: systemic steroids for >5 days, methotrexate, amiodarone, tamoxifen
2. Study:
 - a. Unexpected severe / frequent adverse events

The major outcome choice following the data review by the Board is: 1) continuing the trial unchanged, or 2) modify the protocol and/or consent form, or 3) terminate the trial.

The chairperson ([name]) will be responsible for overseeing the meetings, developing the agenda and summarizing the meeting. The chairperson is the contact person for the DSMB.

The DSMB responsibilities will include:

1. Review of the research protocol, informed consent documents and plans for safety and data monitoring of the study. This review is to determine the risks and benefits to research subjects, protection and safety of the subjects and to offer suggestions for improving the study design.
2. Review interim data to detect adverse effects to determine if the trial should continue as originally designed, should be changed or should be stopped based on the data.
3. Evaluate the progress of the trial including recruitment goals, accrual and retention of participants and other factors that may affect the study outcome.
4. Protect confidentiality of the study participants, trial data and results of the monitoring.

C. Adverse Events Reporting

All treatment emergent serious adverse events will be documented and reported immediately to the IRB at Partners HealthCare System, as well as to the DSMB. An event that is serious must be recorded on the case record and requires expeditious handling to comply with regulatory requirements. In the event that a patient becomes ill or injured as a direct result of participation in the research study, necessary medical care will be made available. All adverse effects will be reported as per Partners Healthcare System requirements. Potentially serious adverse events (SAEs) will be followed to resolution or stabilization and reported as SAEs if they become serious.

A serious adverse event is defined as one that meets any one of the following criteria:

1. Fatal or life threatening
2. Requires inpatient hospitalization
3. Results in persistent or significant disability or incapacity
4. Congenital anomaly
5. Important medical event that may jeopardize the patient or require intervention to prevent serious outcome
6. Cancer
7. Overdose
8. Results in development of drug dependency or drug use

X. REFERENCES

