 - NAFLD Fibrosis Score will be calculated from standard labs and subject characteristics (age, BMI, blood glucose, platelet count and albumin).
 - Serum and Plasma will be collected for future measurement of lipids, bile acids, other metabolites including adipokines and inflammatory markers.
- Additional peripheral blood (serum, plasma, and whole blood) from which we will extract DNA and RNA. This will permit testing (among other things) for the *PNPLA3* rs738409 genotype, as this is an established NAFLD risk locus, and testing of *PNPLA3* is currently recommended in NAFLD/NASH clinical trials⁸.
- Stool samples that have been collected at home will be brought with the patient on the Baseline Visit. A collection kit provided during the Screening Visit will allow minimal contact with the stool and allow easy storage of the sample until the day of the Baseline Visit. If the patient forgets or is unable to complete the sample collection prior to their appointment, they may be given the materials to mail their sample to the study staff.
- MRI: 1H-MRS of the right and left hepatic lobe will be performed to quantify hepatic lipid content and other fat depots. LiverMultiscan sequences will also be performed for noninvasive analysis of hepatic inflammation and fibrosis. During the same MRI session,

MRI-PDFF will also be performed. MRI will be repeated at the 6-month visit (for a total of 2 MRI sessions per subject).

- Fibroscan to measure liver stiffness via transient elastography (ultrasound). Fibroscan will be repeated at the 6-month visit (for a total of 2 Fibroscans per subject).
- Standard bionutrition assessment by trained research nutritionist.
- Assessment of adherence (month 6 visit) by returned pill count and by self-report.
- Three validated questionnaires will be administered to subjects:
 - The Paffenbarger Physical Activity questionnaire
 - The SF-36 health survey questionnaire
 - The semi-quantitative Food Frequency Questionnaire (FFQ)

Total Blood Drawn: Total blood volume from the participant is below 200ml for this Baseline Visit and for the Month 6 visit. As this is below 300ml over at least 6 hours, this does not result in added risk. Normal blood donation volume is 450-500ml.

2. Follow-up 3-month visit: (n=80)

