This visit will be performed during a +/- 2-week interval around the planned date, to accommodate potential scheduling conflicts. A physical examination and measurements of body weight and waist-to-hip ratio will be completed. Study subjects will be assessed for interim medical history, and any side effects to study drug. We will measure a hematocrit.

3. Twice monthly telephone calls or voicemail messages (+/- 1 week):

The trained clinical research coordinator, working directly with the PI, will conduct twice-monthly check-in telephone calls to enrolled subjects on the months when the subject does not have a study visit (i.e. at month 2, month 4 and month 5), using a Partners IRB-approved telephone script. The purpose of these calls will be to ask about medication compliance and to inquire about any concerns or side effects related to the study drug. All subjects will be reminded during this call or voicemail message that the PI ([name]) will be available by pager at all times during the study to answer any questions or concerns that arise.

4. Early Termination Visit:

Subjects who discontinue the study early due to an adverse event, toxicity, or personal reasons will be asked to complete an Early Termination visit. This visit will include all assessments that are performed at the final 6-month visit described above. Participants must have been on the study medication for at least 11 weeks in order to be eligible for completing an Early Termination visit.

5. Remote Visits: Subjects who do not live locally will have the option to perform the 3-month follow-up visit remotely. This will be performed with remote labs (via Quest Diagnostics Locations) and medical history via phone call with a study staff member. For these remote visits, the study staff member will speak to the subject over the phone to review the medical history. If during a phone-medical history, the study staff member believes the subject may be experiencing side-effects related to the study medication, the PI will be notified and the subject will be informed that they need to come to MGH for a physical exam. For these remote visits, the study team will FedEx study medication to the subject in a manner approved by the research pharmacy as needed for resupply. The subject would bring back unused study medication and empty vials to the study team at the next in person visit to maintain standard study drug accountability logs.

B. DRUGS

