To ensure data entry accuracy, peer review of source documentation and case report forms in REDCap will be completed following MGB Study Data Management and Quality Assurance Plan Guidelines. Research coordinators will exchange subject files and review informed consents, case report forms, and adverse event logs for accuracy and completeness. Additionally, eCRFs in REDCap will be reviewed for accuracy and completeness using source data verification.

C. Statistical Analysis and Power

Data Analysis Plan:

This statistical analysis plan will be finalized before database lock. Baseline data between groups will be compared using chi-squared test or Fisher's exact test for categorical variables, and using ANOVA for continuous variables, with any non-normally distributed data log-transformed prior to analysis. If significant baseline group imbalance is detected on any particular variable, that variable will be included as a covariate in the analyses.

Absolute and relative changes in continuous outcomes between treatment groups will be calculated using analysis of covariance (ANCOVA), with treatment group at randomization included as a fixed effect, and the baseline value of the relevant outcome included as a covariate. Logistic regression will be used for binary outcomes (i.e., achievement of $\geq 30\%$ relative HFF reduction). For the primary analysis, all study endpoints will be analyzed using an intention-to-treat approach, using data from all randomly assigned participants in the full analysis set. The primary analysis will assume that missing data were missing at random³⁸, and data augmentation for missing observations will be conducted via multiple imputation, using all available non-missing data of the outcome measurement from the same treatment arm.

We will also utilize data from all participants who adhere to therapy as assigned and complete the final, 6-month visit for study outcomes (i.e., the per protocol analysis set).

We will conduct the following subgroup and sensitivity analyses for the primary and key secondary endpoints:

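### Participants who leave the study before 11 weeks on drug have no post-baseline liver fat value, so the all-80 primary estimate rests for them on same-arm imputation

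*Combined protocol and SAP*

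**What the plan says.** The primary endpoint is the 6-month absolute difference in hepatic fat fraction (HFF) by 1H-MRS. Section V.A places the MRI at baseline and month 6, "for a total of 2 MRI sessions per subject". The 3-month visit has no MRI: "A physical examination and measurements of body weight and waist-to-hip ratio will be completed", with an interim history and a hematocrit.

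The only other route to a scan is the Early Termination visit (Section V.A, Study Visits, item 4): "Subjects who discontinue the study early due to an adverse event, toxicity, or personal reasons will be asked to complete an Early Termination visit". Its content is complete: "This visit will include all assessments that are performed at the final 6-month visit described above". Access is limited: "Participants must have been on the study medication for at least 11 weeks in order to be eligible for completing an Early Termination visit".

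Section VI.C (Data Analysis Plan, Definitions of Analysis Sets) bases the primary analysis on all 80 randomised participants. Missing data are assumed missing at random and filled by "multiple imputation, using all available non-missing data of the outcome measurement from the same treatment arm". A sensitivity analysis carries the baseline value forward.

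The documents do not clearly separate stopping drug from leaving the study. The Risks and Discomforts section removes from the study a subject who starts a medication known to affect liver fat. The Safety Monitoring lists in Section IX give triggers for being discontinued without saying from what. Adherence is checked at the end: "Assessment of adherence (month 6 visit) by returned pill count and by self-report". The per-protocol definition names adherence and month-6 completion as two separate conditions.

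**The concern.** Someone who leaves before week 11 cannot have a termination scan and does not reach month 6, so no HFF is observed after baseline. Same-arm imputation then gives an aspirin leaver the average outcome of aspirin participants who were scanned, most of whom stayed. These leavers had the shortest exposure, so that substitution is least plausible for them. If aspirin lowers liver fat and the benefit fades after stopping, the estimate for all randomised participants is too large.

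A second gap concerns later leavers. They are offered a scan, but no rule says whether a scan taken between week 11 and month 6 stands in for the 6-month value. If it does, it may record a benefit that is gone by month 6.

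**Working it through.** **Inputs from the plan (Section VI.C):** 80 randomised, about 15% drop-out, effect 3 points, SD of change 2.45, two-sided 0.05. **Assumed, not in the documents:** 1:1 allocation, drop-out balanced between arms (6 of 40 in each), placebo change 0, leavers keep no benefit at month 6, and leaving times spread evenly over 26 weeks.

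**1. The plan's own figures.** 80 × 0.85 = 68, or 34 per arm. The standard error is 2.45 × √(2/34) = 0.594. Power at a difference of 3 is 0.999 (noncentral t), consistent with the stated figure of more than 90%.

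**2. True all-randomised effect under the assumptions.** 3 × 0.85 = 2.55.

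**3. Expected primary estimate.** Same-arm imputation is represented by its expectation, the mean of the observed values in that arm. Let u be the share of each arm that is imputed, with all other leavers observed at their true month-6 value. The expected estimate is 2.55 / (1 − u).

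| Situation | u | Estimate | Overstatement |
|---|---|---|---|
| All 12 drop-outs imputed | 0.15 | 3.00 | 0.45 |
| Half of the 12 imputed | 0.075 | 2.76 | 0.21 |
| Only pre-week-11 leavers imputed, even timing | 0.0635 | 2.72 | 0.17 |
| Only 2 of 80 imputed | 0.025 | 2.62 | 0.07 |
| All return at month 6 | 0 | 2.55 | 0 |

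For the third row, 11/26 = 0.423, so 12 × 0.423 ≈ 5 people leave early and u = 0.15 × 0.423 = 0.0635.

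**4. Termination scans counted as 6-month values.** Late leavers make up 0.15 × 15/26 = 0.0865 of each arm. Their mean leaving time is (11 + 26)/2 = 18.5 weeks. With benefit accruing linearly (assumed), the scan shows 18.5/26 = 0.712 of the full effect. The estimate is (2.55 + 0.0865 × 3 × 0.712) / (1 − 0.0635) = 2.92, an overstatement of 0.37.

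**5. Relative to precision.** 0.17/0.594 ≈ 0.3 standard errors, 0.37/0.594 ≈ 0.6 and 0.45/0.594 = 0.76. At the ceiling, coverage of a nominal 95% interval is Φ(1.96 − 0.757) − Φ(−1.96 − 0.757) = 0.88.

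**6. Other assumptions.** If leavers keep half the benefit and all 12 are imputed, the truth is 3 × (0.85 + 0.075) = 2.775 and the overstatement is 0.225. With a true effect of 1.5 and no benefit kept, the ceiling is 1.5 × 0.15 = 0.225. With no true effect it is 0.

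**7. Power.** At a difference of 2.55 with 34 per arm, power is 0.988.

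**8. Baseline carried forward.** With all 12 missing, leavers contribute zero change in both arms, so the result is 0.85 × 3 = 2.55, the truth in this case.

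**The case against.** **The 11-week rule is not the root cause.** A scan at, say, week 6 is not a 6-month HFF, so opening the termination visit earlier would not by itself fill the gap. The values are missing because people leave. This stands, and the remedy should therefore be month-6 collection.

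**A reader might infer that everyone who stops drug is lost to month 6.** The documents do not say so. Checking adherence at month 6, and listing adherence and completion separately, suggest that a non-adherent participant can complete the study. If so, only those who leave the study are affected, and recovering their data depends on their willingness to return.

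**A reader might take 0.45 as the effect of the 11-week rule.** It is a ceiling that needs all 12 drop-outs unscanned and no benefit kept. Leaving times are not given, and with few early leavers the effect is close to nil.

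**A reader might see a risk of a false positive or lost power.** Neither follows: the mechanism adds no bias when aspirin has no effect, and power stays about 0.99.

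**The plan already has a check.** Baseline-carried-forward is pre-specified and recovers 2.55 in the worst case. That is a real mitigation. It remains a single-imputation sensitivity analysis, however: it leaves the primary estimate unchanged and assumes outcomes that could partly be measured.

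**Following everyone to month 6 conflicts with the rule for medications that affect liver fat,** and would bring scans influenced by those drugs into the primary analysis. This stands as a point to reconcile. The plan's intention-to-treat set already includes those participants, so the choice is between observing and imputing their values, and the text should state which.

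**Conclusion.** The gap before week 11 is clear from the text: no post-baseline HFF is available for participants who leave the study by then, and the all-80 estimate relies on same-arm imputation for them. Whether stopping drug ends follow-up, and how termination scans are used, are unstated points to clarify; they are not stated prohibitions.

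The consequence is a modest possible overstatement of a real effect. Under the stated assumptions the working gives about 0.17 points for pre-week-11 leavers alone, about 0.37 with termination scans used as 6-month values, and 0.45 as the ceiling. Confidence is moderate, because leaving times, retained benefit and actual follow-up practice are not in the documents. This is a cheap improvement to the primary estimate, and the trial's test of aspirin against placebo does not depend on it.

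**What to change.** - State that stopping study drug does not by itself end outcome follow-up.
- Invite every randomised participant who still consents and passes MRI screening to the planned month-6 1H-MRS, whatever the weeks on drug, and use those values in the primary intention-to-treat analysis.
- The 11-week condition may stay for the termination visit itself, but it must not limit month-6 outcome collection.
- State in the SAP that a termination scan is a dated auxiliary variable for the imputation and does not serve as the 6-month value.
- Reconcile this with the Risks and Discomforts section and the Safety Monitoring lists by stating whether being discontinued ends outcome collection. The rules for stopping drug are unchanged.
- A placebo-based imputation sensitivity analysis is optional. With placebo change near 0 it has the same expected value as baseline-carried-forward.

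The cost is a short amendment, some SAP wording and retention effort for up to about 12 people. For anyone not already scanned at termination, the month-6 scan is the second session already planned. If a participant scanned at termination also returns at month 6, the two-session wording must allow a third. Some leavers will not return, so some imputation remains: in the ceiling case, if half return, the overstatement falls from 0.45 to 0.21.
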